## **11. DEMOGRAPHIC AND OTHER BASELINE CHARACTERISTICS**

Demographic data and other baseline characteristics will be presented.

The following demographic and other baseline characteristics will be summarized:

- Age (years) at baseline of TED-C13-003
- Age Group – Age is categorized in pre-defined groups: < 1, 1 to <12, 12 to <17, 17 to <18.
- Sex (if female, the reproductive status will be reported)
- Race
- Ethnicity
- Weight Z-score at baseline of TED-C13-003
- Height Z-score at baseline of TED-C13-003
- Body Mass Index (BMI) Z-score at baseline of TED-C13-003

---

Document: \\quintiles.net\Enterprise\Apps\sasdata\SASa\sas\Shire\Teduglutide\ZXA48914\Biostatistics\Documentation\SAP\SHP633-303\_SAP\_Draft\_V1.0\_20171023

Author: [REDACTED]

Version Number:  
Version Date:

Draft V1.2  
16Jan2018

Template No: CS\_TP\_BS016 – Revision 3  
Effective Date: 01May2012

Reference: CS\_WI\_BS005

Copyright © 2012 Quintiles Transnational Corp. All rights reserved.  
The contents of this document are confidential and proprietary to Quintiles Transnational Corp. Unauthorized use, disclosure or reproduction is strictly prohibited.

The demographic data collected in the study eCRF will be listed by subject.

### 11.1. DERIVATIONS

- $BMI \text{ (kg/m}^2\text{)} = 10000 * \text{weight (kg)} / \text{height (cm)}^2$
- Z-score of weight, height, and BMI will be calculated based on the method described in Section 18.7.1.

## 12. MEDICAL HISTORY

Medical history will be presented for the safety population.

### 12.1. MEDICAL AND SURGICAL HISTORY

Medical and Surgical History will supplement the medical history information collected at the start of the TED-C13-003 core study and will consist of the following:

- ongoing adverse events at the time of core study completion
- new medical conditions not related to SBS since core study participation
- Updates to a previously reported medical history

Medical and Surgical History will be coded using **Medical Dictionary for Regulatory Activities (MedDRA)**. Data captured on the Medical and Surgical History page of the CRF will be presented by System Organ Class (SOC) and Preferred Term (PT). SOC will be sorted alphabetically and PT within SOC will be sorted by descending frequency in the any teduglutide (ANY TED) treatment group.

### 12.2. SHORT BOWEL SYNDROME HISTORY

If the subject has any changes to the SBS history collected at the baseline visit of the TED-C13-003 study, that information (updated SBS history) will be collected. The value at the baseline visit of the TED-C13-003 will be used if there is no update for the enrolled subjects in the extension study.

The following SBS History will be summarized:

- Primary reason for the diagnosis of SBS

Document: \\quintiles.net\Enterprise\Apps\sasdata\SASa\sas\Shire\Teduglutide\ZXA48914\Biostatistics\Documentation\SAP\SHP633-303\_SAP\_Draft\_V1.0\_20171023

Author: [REDACTED] Version Number: Draft V1.2  
Version Date: 16Jan2018

Template No: CS\_TP\_BS016 – Revision 3  
Effective Date: 01May2012

Reference: CS\_WI\_BS005

Copyright © 2012 Quintiles Transnational Corp. All rights reserved.  
The contents of this document are confidential and proprietary to Quintiles Transnational Corp. Unauthorized use, disclosure or reproduction is strictly prohibited.

- Presence of stoma; if Y, stoma type
- Presence any remaining colon; if Y, estimated percent colon remaining and whether the colon is in continuity
- Total estimated remaining small intestinal length
- Presence of distal/terminal ileum and ileocecal valve

Date of first major surgical resection, date of last major surgical resection, the secondary reason for the diagnosis for SBS, date of diagnosis of SBS and method of determination for length of remaining anatomy will be presented in the listing only.

## **13. CONCOMITANT TREATMENTS**

Medications and procedures will be presented for the safety population.

Concomitant treatments are defined as all treatments taken between the dates of informed consent and EOS, inclusive. Concomitant treatments include all non-study treatments (medications, herbal treatments, vitamins, invasive and diagnostic procedures). Concomitant treatment information will be recorded on the Prior and Concomitant Medications and Diagnostic/Surgical/Therapeutic Procedures eCRF pages.

### **13.1. CONCOMITANT MEDICATIONS**

Medications will be coded to preferred name using **WHO Drug Dictionary (WHODD)**. Concomitant medication use will be summarized by preferred name using the number and percentage of subjects by treatment group. Medications will be sorted alphabetically by preferred name. Subjects with multiple occurrences of a medication in preferred name will only be counted once within each preferred name. Medication summaries will be presented by treatment group for the safety population.

Listings of all medications will be presented.

### **13.2. DIAGNOSTIC, SURGICAL, OR THERAPEUTIC PROCEDURES**

The diagnostic, surgical, or therapeutic procedures during the study are recorded in the eCRF and will only be presented in a listing.

---

Document: \\quintiles.net\Enterprise\Apps\sasdata\SASa\sas\Shire\Teduglutide\ZXA48914\Biostatistics\Documentation\SAP\SHP633-303\_SAP\_Draft\_V1.0\_20171023

Author: [REDACTED] Version Number: Draft V1.2  
Version Date: 16Jan2018

Template No: CS\_TP\_BS016 – Revision 3  
Effective Date: 01May2012

Reference: CS\_WI\_BS005

Copyright © 2012 Quintiles Transnational Corp. All rights reserved.  
The contents of this document are confidential and proprietary to Quintiles Transnational Corp. Unauthorized use, disclosure or reproduction is strictly prohibited.

## 14. STUDY DRUG EXPOSURE

The overall extent of exposure is defined as the number of days on teduglutide during the core study and prospective observation period combined. Exposure summary will be presented by treatment group (TED/TED, TED/NTT and ANY TED only) as a numeric variable. It will also be categorized and presented in pre-defined groups: 0-<12, 12-<24, 24-<48, 48-<72, 72-<96, 96-<120, 120-<144, 144-<168, >=168 weeks. The overall number of cycles on teduglutide will also be summarized as a numeric variable. Finally, the number of days on teduglutide for each prospective period cycle will be summarized.

### 14.1. DERIVATIONS

The overall extent of exposure in weeks will be calculated as:

Extent of exposure (weeks) = [the exposure days in the core study calculated as (last dose date – first dose date + 1) + the sum of the durations of all the teduglutide treatment periods where the individual duration is calculated by (the last treatment visit of the treatment cycle X – Cycle X Day 1 + 1)] / 7.

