Subjects who previously received teduglutide during TED-C13-003, as well as subjects who were in the standard of care treatment group, may be eligible to receive repeat doses of teduglutide 0.05 mg/kg subcutaneous (SC) once daily injection in this extension study. Subjects not receiving teduglutide treatment (i.e., in a no-teduglutide treatment [NTT] period), will be seen approximately every 12 weeks for safety, PS requirements, and quality of life. The first NTx visit following the screening visit should occur within 2 to 12 weeks of screening. At any point after screening or during a NTT period, subjects who meet at least one teduglutide treatment inclusion criteria, may proceed immediately to the pre-treatment visit if the investigator, subject, and parent agree to proceed with teduglutide therapy.

After the pre-treatment visit, subjects who meet at least one of the teduglutide treatment inclusion criteria, and meet none of the teduglutide treatment exclusion criteria, will start a 28-week cycle, consisting of 24 weeks of teduglutide treatment at 0.05 mg/kg SC once daily, followed by a 4-week follow-up period (during which no teduglutide is administered). During the 28-week cycle, clinic visits will occur at weeks 1, 2, 4, 6, 9, 12, 16, 20, 24, and 28. Phone visits are required approximately 1 week after adjustments in PS during the teduglutide treatment period (between weeks 1 and 24), and weekly during the teduglutide follow-up period (between weeks 24 and 28). Safety and PS requirements will be evaluated at every visit, and quality of life assessments will be made approximately every 12 weeks. If a subject has clinical deterioration and meets follow-up period escape criteria after stopping teduglutide, the subject may "escape" the follow-up period early and proceed immediately to another pre-treatment visit. Following completion of the 28-week treatment cycle, the subject will proceed to an NTT visit within approximately 12 weeks.

Document: \\quintiles.net\Enterprise\Apps\sasdata\SASa\sas\Shire\Teduglutide\ZXA48914\Biostatistics\Documentation\SAP\SHP633-303\_SAP\_Draft\_V1.0\_20171023

Author: [REDACTED]

Version Number:

Draft V1.2

Version Date:

16Jan2018

Template No: CS\_TP\_BS016 – Revision 3

Effective Date: 01May2012

Reference: CS\_WI\_BS005

Copyright © 2012 Quintiles Transnational Corp. All rights reserved.

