## **10. DISPOSITION AND WITHDRAWALS**

All subjects who provide informed consent for prospective data collection in the extension study will be accounted for in the analyses. After signed consent (and informed assent, if applicable), a subject will be considered enrolled in the study if the subject meets all of the inclusion criteria at the screening. Teduglutide treatment eligibility does not impact study eligibility.

If the investigational product is discontinued prematurely during a teduglutide treatment cycle and the subject wishes to remain in the study, the evaluations listed for the EOT visit are to be performed. A 4-week follow-up period will ensue, consisting of weekly telephone visits (CxW25-27) and the week 28 clinic visit (CxW28). The subject would then enter a NTT period and could be evaluated for subsequent teduglutide treatment eligibility according to the study

Document:	\quintiles.net\Enterprise\Apps\sasdata\SASa\sas\Shire\Teduglutide\ZXA48914\Biostatistics\Documentation\SAP\SHP633-303_SAP_Draft_V1.0_20171023		
Author:	[REDACTED]	Version Number:	Draft V1.2

Template No: CS\_TP\_BS016 – Revision 3  
Effective Date: 01May2012

Reference: CS\_WI\_BS005

Version Date:  
16Jan2018

Copyright © 2012 Quintiles Transnational Corp. All rights reserved.  
The contents of this document are confidential and proprietary to Quintiles Transnational Corp. Unauthorized use, disclosure or reproduction is strictly prohibited.

schedules. The reason for permanent treatment discontinuation will be captured.

The reason(s) for permanent discontinuation of treatment and/or withdrawal from the study must be determined by the investigator, and recorded in the subject's medical record and in the electronic case report form (eCRF). If a subject is withdrawn for more than one reason, each reason should be documented in the source document, and the most clinically relevant reason should be entered in the eCRF. Overall reasons for discontinuation of treatment and withdrawal from study will be summarized separately based on the following categories:

- Adverse event
- Protocol deviation
- Lack of efficacy
- Physician decision
- Withdrawal by subject
- Withdrawal by parent/guardian
- Lost to follow-up
- Pregnancy
- Death
- Other

The ongoing subjects will be counted in the table for interim analysis.

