## 15. STUDY DRUG COMPLIANCE

Study drug administration diary data will be used to measure study drug compliance. Only diary entries with “Yes” in response to the question “Was the study drug administered per instructions today?” will be deemed compliant days.

Subjects will be considered compliant overall for study drug administration if the calculated compliance is >= 80% for each treatment period. Overall and by-cycle treatment compliance will be presented for percent compliance calculations using descriptive statistics and the number and percentage of subjects entering the timeframe who are >= 80% compliant by treatment group for the safety population.

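### Prospective-cycle exposure ends at a visit rather than at the last dose, which miscounts days on teduglutide for subjects lost between visits and for some early stoppers

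*SAP*

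**What the plan says.** Prospective SAP, section 14, sets the quantity to be measured: "The overall extent of exposure is defined as the number of days on teduglutide during the core study and prospective observation period combined". It adds a second output on the same basis: "the number of days on teduglutide for each prospective period cycle will be summarized". The combined total is also tabulated in bands with cuts at 12, 24, 48, 72, 96, 120, 144 and 168 weeks.

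Section 14.1 gives the formula, which has two terms:

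- Core study: "the exposure days in the core study calculated as (last dose date – first dose date + 1". This term uses dose dates.
- Each prospective cycle: "the last treatment visit of the treatment cycle X – Cycle X Day 1 + 1". This term uses visit dates.

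The SAP does not define *last treatment visit*. Section 10 provides for early stopping ("If the investigational product is discontinued prematurely during a teduglutide treatment cycle and the subject wishes to remain in the study") by calling for the EOT evaluations. It states no interval from the last dose and does not say whether that visit is the last treatment visit. Section 10 also lists loss to follow-up among the reasons for discontinuation. Section 7.5 covers only how EOT visits are mapped or tabled.

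A daily dosing record exists. Section 15 says: "Study drug administration diary data will be used to measure study drug compliance".

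**The concern.** The formula adds two different quantities under one name. Its prospective term equals days on teduglutide only when the last dose falls on the date of the last treatment visit. The other exposure terms in the two plans do not have this feature: core-study days use dose dates, and section 13.1 of the retrospective SAP uses prescription start and stop dates.

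Long-term safety is the primary objective (section 3.1), and the exposure table tells the reader how much drug lies behind the safety data. Any error falls mainly on subjects who stop early or drop out. Their time on drug is of particular interest when individual adverse events are read, and with about 40 subjects expected (section 4.1) a single subject in the wrong band shows in the table.

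Because the key term is undefined, two programmers could also derive different values for the same early stopper.

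**Working it through.** The SAP gives no exposure figure to reproduce, so the check is date arithmetic on its own schedule.

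**Inputs.** Visit schedule from section 4.1: "clinic visits will occur at weeks 1, 2, 4, 6, 9, 12, 16, 20, 24, and 28". Visit window of 4 days either way for weeks 9 to 24, from section 7.5. Exposure bands from section 14. Assumptions: the first dose is on Cycle X Day 1, and the nominal visit in week w falls on cycle day 7w + 1.

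**Formulas.** SAP days = cycle day of the last treatment visit. Dose-based days = cycle day of the last dose, which is the core-study rule applied to a cycle.

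**Subject lost between visits.** The last attended visit is week a, and dosing continues to the day before the planned visit in week b (worst case). SAP days = 7a + 1, dose-based days = 7b, and shortfall = 7(b − a) − 1.

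| Weeks a to b | SAP days | Dose-based days | Shortfall | Share of dose-based days |
|---|---|---|---|---|
| 6 to 9 | 43 | 63 | 20 | 31.7% |
| 9 to 12 | 64 | 84 | 20 | 23.8% |
| 12 to 16 | 85 | 112 | 27 | 24.1% |
| 16 to 20 | 113 | 140 | 27 | 19.3% |
| 20 to 24 | 141 | 168 | 27 | 16.1% |

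Earlier gaps give at most 6 days (1-week gaps) or 13 days (2-week gaps). If the first visit of a 4-week gap is 4 days early and dosing runs to the day before a visit planned 4 days late, the shortfall is 27 + 4 + 4 = 35 days. This undercount does not depend on how *last treatment visit* is read, because the subject has no EOT visit.

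**Early stopper.** Take a last dose on day 60 as an example. The SAP gives no lag to the EOT visit, so a range is assumed.

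- If the EOT visit counts, SAP days = 60 + lag. Lags of 0, 7, 14 and 28 days give 60, 67, 74 and 88 days, or errors of 0%, +11.7%, +23.3% and +46.7%.
- If only visits on drug count, the last one is week 6 (day 43). The SAP gives 43 days, which is 60 − 43 = 17 days too few (17/60 = 28.3%).

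**Completer.** The nominal week 24 visit is day 169. With the last dose the day before, true exposure is 168 days and the error is +1. With a dose on the visit day, the error is 0.

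**Bands.** These apply to core plus prospective exposure, and the SAP gives no core-study duration. With an assumed 12 weeks of core exposure and loss between weeks 9 and 12, the SAP gives 12 + 64/7 = 21.1 weeks (band 12 to <24), against 12 + 84/7 = 24.0 weeks (band 24 to <48). For each assumed core exposure of 4, 8, 12, 16, 20 or 24 weeks, at least one such worst-case loss during the first cycle moves a subject down one band.

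**The case against.** The strongest reply is that the effect is small and partly unknown. Exposure is descriptive: section 8.4 rules out hypothesis testing, and section 18.1 reports adverse events as numbers and percentages of subjects and as event counts. No exposure-adjusted rate is described, so the figure enters no stated safety denominator. The SAP does not say how many subjects stop early or are lost. All of this stands and limits the weight of the point, but the formula still does not deliver the quantity that section 14 defines.

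A reader might go further and infer that the 4-day window at week 24 gives completers anything from 165 to 173 days, so that whole cycles fall on either side of the 24-week cut. The documents do not support that. The legend to Table A in section 4.1 has subjects stop teduglutide at week 24, and the SAP nowhere fixes dosing at 168 days regardless of the visit. If dosing stops at the visit, an earlier or later visit means truly shorter or longer dosing. A single cycle also cannot be set against the 24-week cut, because the bands include core-study days and section 6 says that no treatment-naïve core-study patients enrolled.

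A reader might also infer that early stoppers are always overcounted. That holds only if the EOT visit is the last treatment visit and comes after the last dose. On the other reading the error reverses.

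A third objection concerns the remedy. The diary question in section 15 asks whether the drug was given per instructions, so the last affirmative day is not necessarily the last dose. Nor does the SAP say that diary pages after the last attended visit will be retrieved. Both points stand and shape the fix.

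**Conclusion.** The point holds in limited form. As written, section 14.1 undercounts a subject lost between visits by up to 20 days in a 3-week gap and 27 days in a 4-week gap on the nominal schedule. These are worst cases that assume dosing continued to the day before the next planned visit. For early stoppers the sign and size of the error depend on an undefined term and an unstated lag, and the error is zero when the EOT visit falls on the last dose day. Completers are affected by about one day.

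Shifts between bands are possible, but they were shown only under assumed core-study durations. Nothing here biases a test or a stated event rate. It is a correctable flaw in a descriptive safety summary and worth repairing because the repair is cheap.

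**What to change.** In section 14.1, replace the cycle term with (last dose date in cycle X – first dose date in cycle X + 1), so that both terms use dose dates.

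- **Source.** Take the last dose date from the eCRF if it is recorded there. Otherwise use the last diary day showing any administration, not only a day marked as given per instructions. Check whether the diary separates these two cases.
- **Fallback.** Where the diary is missing, or stops before the last attended on-treatment visit with no recorded discontinuation, use that visit date and flag the cycle. A fallback limited to cycles with no diary at all would not be enough. A completer whose diary breaks off at week 12 would be given about 84 days instead of about 168, a larger error than the 27 days being corrected.
- **Consistency.** Apply the same end date to the per-cycle summary in section 14. Reconcile it with the compliance denominator in section 15.1, which runs to the last visit date of the cycle. Since the cycle lasts 28 weeks with 4 weeks off drug, that wording could be read to include follow-up visits.

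The cost is a few lines of SAP text and a small derivation change, with no new data collection; the prospective SAP is still marked Draft V1.2. The downside is that some cycles with incomplete diaries will rest on the flagged fallback. For a lost subject whose later diary pages are never retrieved, the undercount will remain but will be visible.

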## 15. STUDY DRUG COMPLIANCE

Study drug administration diary data will be used to measure study drug compliance. Only diary entries with “Yes” in response to the question “Was the study drug administered per instructions today?” will be deemed compliant days.

Subjects will be considered compliant overall for study drug administration if the calculated compliance is >= 80% for each treatment period. Overall and by-cycle treatment compliance will be presented for percent compliance calculations using descriptive statistics and the number and percentage of subjects entering the timeframe who are >= 80% compliant by treatment group for the safety population.

### 15.1. DERIVATIONS

For each treatment cycle and overall, compliance will be calculated as the number of doses administered divided by the planned number of doses expressed as a percentage. This can be summarized as:

Percent compliance = (Total number of diary days marked “Yes” for study drug

---

Document: \\quintiles.net\Enterprise\Apps\sasdata\SASa\sas\Shire\Teduglutide\ZXA48914\Biostatistics\Documentation\SAP\SHP633-303\_SAP\_Draft\_V1.0\_20171023

Author: [REDACTED] Version Number: Draft V1.2  
Version Date: 16Jan2018

Template No: CS\_TP\_BS016 – Revision 3  
Effective Date: 01May2012

Reference: CS\_WI\_BS005

Copyright © 2012 Quintiles Transnational Corp. All rights reserved.  
The contents of this document are confidential and proprietary to Quintiles Transnational Corp. Unauthorized use, disclosure or reproduction is strictly prohibited.

administration / Number of days on treatment) \* 100

where number of days on treatment within each cycle will be calculated as (the last visit date in the treatment cycle X - the visit date of Cycle X Day 1 +1) and dose interruption days will not be excluded.

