## 7.4. STUDY CYCLE CONVENTIONS

Visits will be summarized within the associated pretreatment period or treatment cycle or no treatment period. For teduglutide treatment cycles, Cycle x Day 1, Cycle x Week 1, ..., Cycle x Week 24, Cycle x Week 25 Follow-up, Cycle x Week 26 Follow-up, Cycle x Week 27 Follow-up and Cycle x Week 28 data will be collected according to the schedule of events.

For NTT periods, NTx data will be collected approximately every 12 weeks. Data for teduglutide treatment periods and NTT periods will be presented in separate tables.

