## 7.5. WINDOWING CONVENTIONS

For teduglutide treatment period, nominal visits will occur within two days of the scheduled week 1, 2, 4 and 6 visits, within four days of the scheduled week 9 to week 24 visits and within two days of the follow-up visits week 25 to week 28 (EOS). For NTT period, nominal visits will occur within seven days of the scheduled 12-week intervals. There will be no windowing of scheduled visits based on study day, and unscheduled visits will not be included in by-visit summaries. Early termination data and end of treatment (EOT) visits with a teduglutide treatment cycle will be mapped to a scheduled visit if it falls into the appropriate visit window as defined in the protocol and if that scheduled visit did not occur. EOT visits, if occurring differently from week 24 will be tabled as a separate visit.

---

Document: \\quintiles.net\Enterprise\Apps\sasdata\SASa\sas\Shire\Teduglutide\ZXA48914\Biostatistics\Documentation\SAP\SHP633-303\_SAP\_Draft\_V1.0\_20171023

Author: [REDACTED] Version Number: Draft V1.2  
Version Date: 16Jan2018

Template No: CS\_TP\_BS016 – Revision 3  
Effective Date: 01May2012

Reference: CS\_WI\_BS005

Copyright © 2012 Quintiles Transnational Corp. All rights reserved.  
The contents of this document are confidential and proprietary to Quintiles Transnational Corp. Unauthorized use, disclosure or reproduction is strictly prohibited.

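### Prospective SAP 15.1: the compliance denominator runs to the last visit of the cycle, so drug-free follow-up counts as treatment time and full adherence scores 85.3%

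*SAP*

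**What the plan says.** All references are to the prospective SAP.

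- **Section 15.1** first describes compliance as doses administered over planned doses. It then gives the working formula: diary days marked Yes over days on treatment, where "number of days on treatment within each cycle will be calculated as (the last visit date in the treatment cycle X" minus the Cycle X Day 1 visit date, plus 1). Days of dose interruption stay in the denominator. Nothing is said about removing follow-up days.
- **Section 15** sets the threshold: "Subjects will be considered compliant overall for study drug administration if the calculated compliance is >= 80% for each treatment period". It also promises overall and by-cycle compliance, with the number and percentage of subjects at or above 80%.
- **Section 4.1** defines the cycle: eligible subjects "will start a 28-week cycle, consisting of 24 weeks of teduglutide treatment at 0.05 mg/kg SC once daily, followed by a 4-week follow-up period", with no drug given in those last four weeks. A subject who deteriorates may leave the "follow-up period early and proceed immediately to another pre-treatment visit".
- **Section 7.4**, on treatment cycles, lists the follow-up visits among the cycle's visits: "Cycle x Week 27 Follow-up and Cycle x Week 28 data will be collected according to the schedule of events".
- **Section 7.5**, under the teduglutide treatment period, sets visit windows that include "within two days of the follow-up visits week 25 to week 28 (EOS").
- **Section 10** gives the same tail to subjects who stop drug early and stay in the study: "A 4-week follow-up period will ensue, consisting of weekly telephone visits (CxW25-27) and the week 28 clinic visit (CxW28").
- **Section 14.1** computes exposure over a span that also starts at Cycle X Day 1 but ends it at "the last treatment visit of the treatment cycle X".
- **Section 16** equates the end of a teduglutide treatment cycle with Week 24 or EOT.

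**The concern.** The numerator can contain only days on which drug was given. The denominator, read as written, also contains the follow-up weeks in which none is given. A completed cycle therefore cannot score near 100%, and the score depends on how long the subject was followed after the last dose as well as on adherence.

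The distortion is uneven. Cycles with full follow-up lose most, and cycles cut short by escape lose less. Cycles that end at EOT, or are still in dosing at the interim analysis, lose essentially nothing. The by-cycle summary and the 80% row would pool these. Because Section 15 requires 80% in every treatment period, one adherent cycle that falls below the line for this reason is enough to class the subject as non-compliant overall.

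**Working it through.** The plan states no compliance figure, so there is nothing to reproduce. The formula was applied to the plan's own schedule.

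**Inputs**
- Planned doses: 24 weeks once daily (Section 4.1), 24 × 7 = 168.
- Cycle length: 28 weeks (Section 4.1), so Week 28 falls 28 × 7 = 196 days after Day 1.
- Window for Weeks 25 to 28: ±2 days (Section 7.5).
- Threshold: 80% (Section 15).
- Assumptions: visits on schedule unless stated, and 168 dosing days available. About 90% adherence is taken as 151 doses (151/168 = 89.9%).

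**Denominator with k weeks of follow-up:** 168 + 7k + 1 = 169 + 7k.

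| Last visit in cycle | Denominator | Full adherence (168) | 151 doses | Doses needed for 80% |
|---|---|---|---|---|
| Week 24/EOT (k = 0) | 169 | 99.4% | 89.3% | 136 (81.0% of 168) |
| Week 25 (k = 1) | 176 | 95.5% | 85.8% | 141 (83.9%) |
| Week 26 (k = 2) | 183 | 91.8% | 82.5% | 147 (87.5%) |
| Week 27 (k = 3) | 190 | 88.4% | 79.5% | 152 (90.5%) |
| Week 28 (k = 4) | 197 | 85.3% | 76.6% | 158 (94.0%) |

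The Week 25 to 27 rows assume that the last visit before an escape is the weekly phone visit.

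**Effect of the window at Week 28.** The denominator runs from 195 to 199 days. Full adherence gives 168/195 = 86.2% down to 168/199 = 84.4%. Exactly 90% of 168 (151.2) gives 77.5% down to 76.0%, below 80% throughout.

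**Early stop with the Section 10 follow-up, no dose missed before the stop at Week w:** 7w / (7w + 28 + 1).
- Week 12: 84/113 = 74.3%, fails.
- Week 16: 112/141 = 79.4%, fails.
- Week 17: 119/148 = 80.4%, passes.

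Moving the last visit by 2 days changes the two results nearest the line: Week 16 becomes 112/139 = 80.6% and Week 17 becomes 119/150 = 79.3%. The Week 12 result stays below 80% either way (84/111 = 75.7%, 84/115 = 73.0%).

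**The case against.** The best defence is that Week 24 was meant. The denominator is labelled days on treatment and is introduced as the planned number of doses. Section 16 takes Week 24 or EOT as the end of the treatment cycle. Section 15 applies the 80% rule per treatment period, which Section 4.1 describes as weeks 1 to 24, separate from follow-up. A programmer who followed those cues would misclassify nobody on account of follow-up.

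That shows probable intent but does not repair the rule. The section that sets cycle conventions puts Week 28 in the treatment cycle, and Section 7.5 lists the follow-up visits even under the treatment period. Section 14.1 specifies the last *treatment* visit, while Section 15.1 drops that word. For the same fully adherent subject the two readings give 99.4% and 85.3%. For the same subject with 151 doses, one reading passes and the other fails.

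Four narrower objections have force:
- This is an inconsistent definition, not a miscalculated number in the plan.
- The Week 27 failure depends on rounding down: 152 doses give 152/190 = 80.0%, which passes.
- The early-stop figures near 80% depend on visit timing. They also assume that planned doses end when treatment stops, which the plan does not say; against all 168 doses a Week 12 stop would score 84/168 = 50%.
- The consequence is small: the safety population does not depend on compliance, and exposure uses a different end date.

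None of these touches the result for a completed cycle.

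**Conclusion.** The concern holds. As written, the denominator in Section 15.1 contradicts that section's own reference to planned doses and the end point used in Section 14.1. For a completed cycle with on-schedule visits and 168 dosing days, full adherence is reported as 85.3% (84.4% to 86.2% across the Week 28 window). The nominal 80% threshold acts as a 94.0% threshold, and a subject at 90% adherence is classed as non-compliant.

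The error shrinks with earlier escape. Where the last visit is Week 24 or EOT, only the extra day from the +1 remains. The affected output is descriptive and feeds no analysis set, efficacy result or safety result. It should be corrected before the plan is finalised, but it does not threaten the study's conclusions.

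**What to change.** In Section 15.1, define days on treatment in cycle X as the date of the last treatment visit (Week 24 or EOT, as in Section 14.1) minus the Cycle X Day 1 visit date, plus 1. State that follow-up Weeks 25 to 28 are excluded and that dose interruption days are still not excluded.

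On schedule this gives 168/169 = 99.4% for full adherence and 151/169 = 89.3% for 151 doses. It still differs by one day from the 168 planned doses. If exact agreement is wanted, the span can end on the last planned dose day instead. The same sentence should say that, for a subject who stops early, planned doses are counted only to EOT, because this definition implies it.

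The cost is one line of SAP text and one date variable in the program. No new data are needed, and the prospective SAP is still at Draft V1.2.
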